17.1. General Considerations

Two analysis cohorts have been defined for this study:

- PMA-S cohort (US/Canada/Europe cohort) – subjects from US, Canada, and Europe centers
- PMDA cohort (US/Canada/Europe/Japan cohort) – subjects from US, Canada, Europe, and Japan centers

Analysis methods are detailed for all objectives in sections 17.1- 17.5. The same methods will be used for both the PMA-S cohort, and also the PMDA cohort. The estimated sample sizes are 150 subjects for the PMA-S cohort, and 165 subjects for the PMDA cohort. The PMDA cohort will have a slight increase in statistical power given 165 subjects will be utilized versus 150.

The Statistical Analysis Plan (SAP) will be created prior to data analysis and include a comprehensive description of the statistical methods to be included in study reports. Any change to the data analysis methods described in the CIP will require an amendment only if it changes a principal feature of the CIP. Any other change to the data analysis methods described in the CIP, and the justification for making the change, will be described in the clinical study report. Medtronic employees or their designated representatives will perform all statistical analyses.

17.2. Analysis Timing

17.2.1. PMA-S Submission

At the completion the last 12 month visit from the enrolled and treated US, Canada and Europe subjects, a PMA-S will be submitted to the FDA. Study data from the Japanese centers will not be included in the PMA-S submission but will be made available.

17.2.2. PMDA Submission

At the completion the last 12 month visit from the enrolled and treated Japan subjects, a report will be submitted to Japan PMDA. Study data from all enrolled and treated subjects (US, Canada, Europe, and Japan) will be included.

17.3. Primary Objectives

17.3.1. Primary Efficacy Objective

Demonstrate an acceptable efficacy success rate at 12 months after the pulmonary vein isolation (PVI) ablation procedure.

Hypothesis

The following hypothesis will be tested in a one-sided test at the 0.025 significance level:

Medtronic Confidential

Ho: PS \leq 40%

Ha: PS $>$ 40%

Where PS is the probability of treatment success at 12 months.

Endpoint Definition

Treatment success is defined as freedom from treatment failure. Treatment failure is defined as any of the following components:

- Acute procedural failure
- Documented AF/AT/ AFL on Holter/TTM/12-lead ECG after the 90 day blanking period
 - Minimum of 30 seconds on Holter/TTM and 10 seconds on 12-lead ECG
- A reablation for the treatment of recurrent AF/AT/AFL after the 90 day blanking period
- Class I or III antiarrhythmic drug (AAD) dose increase from the historic maximum ineffective dose (prior to the ablation procedure) or initiation of a new Class I or III AAD after the 90 day blanking period. Note: remaining on the same pre-ablation dose or decreased dose, or re-initiation of a previously failed or not tolerated Class I or III AAD after the 90 day blanking is not considered a failure. Subjects are allowed to remain on Class I or III antiarrhythmic medications at the historic maximum ineffective dose (on prior to the ablation procedure) after the 90 day post-procedure blanking period.
- Ablation using RF in the left atrium

Blanking period is defined as the first 90 days after the index ablation procedure. Recurrences of atrial arrhythmias during the blanking period will not be counted in the determination of the first clinical failure for the primary endpoint. Within the blanking period, recurrent arrhythmias can be managed with antiarrhythmic drugs, cardioversion or one cryo re-ablation procedure of the pulmonary veins. Titration of Class I and III antiarrhythmic medications are allowed during the blanking period.

Acute procedural failure is defined as:

- Inability to isolate all accessible targeted pulmonary veins (minimally assessed for entrance block and, where assessable, exit block) during the index procedure
- Left atrial non-PVI ablations including but not limited to, ablation of linear lesions, complex fractionated electrograms or non-PV triggers

Analysis Methods

The probability of a subject achieving effectiveness success at 12 months (365 days) will be estimated using survival analysis, the Kaplan-Meier method. The standard error will be approximated using Greenwood's formula. A two-sided 95% log-log confidence interval for the probability will be constructed.

For every treated subject, day 0 is defined as the day of the index cryoablation procedure. For subjects with treatment failure, the survival date will be set to the date of the treatment failure. For subjects without treatment failure through 12 months, those subjects will be censored at the last study contact date

Medtronic Confidential

recorded on CRF which may include the last study visit, the exit date, or death date. If a subject without a treatment failure is lost to follow-up, the censoring date will be set to the last known study visit date.

For the component of the endpoint, documented AF/AT/AFL, if this documentation resulted from rhythm monitoring occurring at the 12-month visit within the 12-month visit window, the date of recurrence will be set to 365 days from the study ablation procedure so that these events will be counted as treatment failures in the 12-month Kaplan-Meier analysis.

Performance Requirements

If the lower bound of the 95% confidence interval at 12 months is greater than the performance goal of 40%, the objective will be considered met.

Rationale for Performance Criteria

The choice of twelve month follow-up and acceptable success rate of 40% performance criteria was selected based on the 2012 HRS/EHRA/ECAS Expert Consensus Statement on Catheter and Surgical Ablation of Atrial Fibrillation: Recommendations for Patient Selection, Procedural Techniques, Patient Management and Follow-up, Definitions, Endpoints, and Research Trial Design, provides recommendations for success rates in clinical trials. The recommendation for evaluating the efficacy of a treatment for persistent AF is as follows: *"If minimum chronic success rate is selected as an objective effectiveness endpoint for a clinical trial, we recommend that the minimum chronic acceptable success rate for persistent AF at 12-month follow-up is 40%."*¹

Additionally, there is mounting evidence in published literature on the use of catheter ablation in the treatment of persistent AF. Table 12 displays a summary of published literature where the publications reported on utilizing Arctic Front and Arctic Front Advance catheters for the treatment of patients with persistent AF. The summary includes results published as manuscripts in peer reviewed medical journals. The search criteria were publications on studies where the therapy was the use of the Cryoballoon for a PVI-only approach for persistent AF. There were variations in endpoint definitions and use of antiarrhythmic medications in the reported studies, but on average the data support the criteria from the 2012 HRS/EHRA/ECAS Expert Consensus Statement. A weighted average was calculated at the bottom of the table, resulting in an average efficacy rate of 59.3%. None of the studies utilized weekly TTMs, so due to the additional arrhythmia monitoring, the point estimate for this study has been set to 54%. The weighted average lower 95% confidence bound is 43.8%, and in combination of additional arrhythmia monitoring, support the lower confidence bound OPC of 40%.

STOP Persistent AF Clinical Investigation Plan

Version 6, 01DEC2017

Page 67 of 128

Table 12: Summary of Published Literature on Catheter Ablation for Persistent AF

Reference	Design	Sites	Subjects	Subject Monitoring (When/How)	Efficacy Arrhythmia Assessment	12M Efficacy*	Off AADs?	Acute Procedural Success
Aytemir K, et al J Interv Card Electrophysiol 2013;38(3):187-195. ⁱ	Prospective, observational, consecutive patients, PVI-only	1	48	ECG and 24hr Holter @ 3M,6M,12M and symptomatic event recorder	AF > 30s	0.62 (0.47, 0.76)	YES	99.50%
Ciconte G, et al Heart Rhythm. 2014; 12(1):60-6. ⁱⁱ	Prospective, consecutive patients, PVI-only	3	63	ECG and 24hr Holter @ 1M,3M,6M,12M	Any AF/AT > 30s	0.60 (0.47, 0.72)	YES	100%
Ferrero-De Loma-Osorio A., et al J. Intervent. Card. Electrophysiol. August 1 2013;37(2):189-196. ⁱⁱⁱ	Prospective, consecutive patients, PVI-only	1	23	3M and every 6 thereafter (72h Holter + ECG)	AF > 30s	0.49 (0.27, 0.69)	YES	96.80%
Jackson N, et al Heart Lung Circ 2012;21(8):427-432. ^{iv}	Consecutive patients, PVI-only	1	61	3M,6,12 (unspecified duration Holter + ECG)	AF > 30s	0.59 (0.46, 0.71)	YES	97.70%
Kojodjojo P, et al Heart 2010;96(17):1379-1384. ^v	Prospective, consecutive patients	1	34	3M,6,12 and every 6 thereafter (24h Holter + ECG +symptomatic event recorder)	Any AF/AT > 30s	0.48 (0.30, 0.65)	YES	83%
Kubala M, et al Clin Electrophysiol 2011;34(7):837-843. ^{vi}	Prospective, consecutive patients, PVI-only	1	33	ECG and 24hr Holter @ 1M,3M,6M,12M and symptomatic event recorder	AF > 30s	0.52 (0.34, 0.69)	YES	Not reported

Medtronic Confidential

STOP Persistent AF Clinical Investigation Plan

Version 6.0, 01DEC2017 Page 68 of 128

Malmborg H, et al Europace 2013;15(11):1567-1573. ^{vii}	Prospective, randomized, PVI-only	1	15	ECG @ 3M,6,12 and 7 day Holter @ 6M,12M	AF > 30s	0.60 (0.32, 0.84)	NO	98%
Neumann T, et al J Am Coll Cardiol 2008;52(4):273-278 ^{viii}	Prospective, consecutive patients, PVI-only	3	53	7 day Holter @ 3M,6M,9M,12M	AF > 30s	0.42 (0.28, 0.56)	YES	97%
Schmidt M, et al Int J Cardiol 2013;167(1):114-120 ^{ix}	Consecutive patients, PVI-only	3	44	ECG and 72hr Holter @ 1M,3M,6M,9M,12M and symptomatic event recorder	AF or Flutter >30s	0.77 (0.62, 0.89)	YES	100%
Schmidt M, et al Clin Res Cardiol 2012;101(10):777-785. ^x	Prospective, consecutive patients, PVI-only	1	33	ECG and 72hr Holter @ 1M,3M,6M,9M,12M and symptomatic event recorder	AF > 30s	0.70 (0.51, 0.84)	NO	98.40%
Lemes C, et al Europace. 2015 May 19. [Epub ahead of print]. ^{xi}	Retrospective, PVI-only	2	49	Holter and ECG and telephonic interviews @ 3M,6M,12M	Any AF/AT > 30s	0.69 (0.57, 0.83)	YES	100%
Weighted average (weights based on study sample size)						59.3% (43.8, 74.4%)		

*Confidence interval calculated with binomial Fisher's exact methods

Medtronic Confidential

Sample Size Calculation

For the US/Canada/Europe cohort, 150 treated subjects affords 90% power based on the following assumptions:

- One analysis at 12-months
- 12-month efficacy rate = 54%
- OPC = 40% at 12-months
- Overall alpha = 0.025, one-sided
- 10% attrition through 12 months
- Binomial exact methods

Table 12 summarizes the published literature of 12-month efficacy rates for Cryoballoon PVI ablation. The summary estimates 12-month efficacy to be 59.3%. Due to more stringent endpoint definition, increased monitoring, and the potential for publication bias, this study protocol assumes a 12 month efficacy rate of 54% for the sample size calculation. With 150 enrolled and treated subjects, minus an assumed 10% attrition rate, the expected number of subjects with 12 months of follow-up at the final analysis is 135.

For the US/Canada/Europe/Japan cohort, 165 treated subjects affords 92% power to test the primary endpoint based on the same assumptions. With 165 enrolled and treated subjects, minus an assumed 10% attrition rate, the expected number of subjects with 12 months of follow-up at the final analysis is 148.

Determination of Subjects/Data for Analysis

All enrolled subjects who have the Arctic Front Advance Cardiac CryoAblation Catheter inserted into vasculature will be included.

Sensitivity Analyses

A sensitivity analysis will be conducted to estimate the potential impact of subjects with less than 12 months of follow-up at the final analysis. The mortality rate in this patient population is anticipated to be low. The total assumed attrition rate through one year is 10%. Because the primary endpoint will be tested using survival methods, all treated subjects are included in the primary analysis, and therefore no subjects will have complete missing data. For subjects that exit early, a tipping point analysis will be conducted to estimate the potential impact of subjects with less than 12-months of follow-up. These subjects will be defined as subjects with partial data. The tipping point analysis methods will be as follows. For each subject with less than 12-months of follow-up, each subject will be set to treatment failure (failure date set to date of study exit). The 12-month Kaplan-Meier estimate will be re-calculated with the earliest (closest to index ablation) sequentially added to the Kaplan-Meier analysis, and the results presented in table format. The tipping point will be defined as the number of additional failures in which the 40% OPC is crossed by the lower 95% confidence bound.

Medtronic Confidential

17.3.2. Primary Safety Objective

Demonstrate an acceptable safety profile of the pulmonary vein isolation (PVI) ablation procedure.

Hypothesis

The following hypothesis will be tested in a one-sided test at the 0.025 significance level:

Ho: $P_S \geq 13\%$

Ha: $P_S < 13\%$

Where P_S is the probability of a safety event through 12 months.

Endpoint Definition

A primary safety event is defined as a serious procedure-related or serious system-related adverse event including the following:

- Transient ischemic attack (within 7 days of ablation procedure)
- Cerebrovascular accident (within 7 days of ablation procedure)
- Major bleeding that requires transfusion (within 7 days of ablation procedure)
- Cardiac perforation, tamponade or pericardial effusion (within 7 days of ablation procedure)
- Pulmonary vein stenosis (>75% reduction within 12-months of ablation procedure)
- Myocardial infarction (within 7 days of ablation procedure)
- Phrenic nerve injury (unresolved at 12-months)
- Atrio-esophageal fistula (within 12-months of ablation procedure)
- Death (within 7 days of ablation procedure)

Analysis Methods

The probability of a safety event at 12 months (365 days) will be estimated using survival analysis, the Kaplan-Meier method. The standard error will be approximated using Greenwood's formula. A two-sided 95% log-log confidence interval for the probability will be constructed.

For every treated subject, day 0 is defined as the day of the index cryoablation procedure. For subjects with a safety event, the survival date will be set to the date of the safety event. For subjects without a safety event, those subjects will be censored at the last study contact date recorded on CRF which may include the last study visit, the exit date, or death date. If a subject without a safety event is lost to follow-up, the censoring date will be set to the last known study visit date.

For subjects with a repeat ablation within 12 months, the start of the survival analysis will not reset. Day 0 will remain the day of the index cryoablation procedure. Safety events related to the repeat ablation procedure occurring on or prior to 365 days post the index cryoablation procedure will be counted as safety events and count against the primary safety objective.

Performance Requirements

If the upper bound of the two-sided 95% confidence interval at 12 months is less than the performance goal of 13%, the objective will be considered met.

Determination of Subjects/Data for Analysis

All enrolled subjects who have the Arctic Front Advance Cardiac CryoAblation Catheter inserted into vasculature will be included.

Sample Size Calculation

For the US/Canada/Europe cohort, 150 treated subjects affords 86% power based on the following assumptions:

- One analysis at 12-months
- 12-month safety rate = 5%
- Clinically important difference = 8% (i.e., if the safety rate of the cryoballoon in this population is 5%, the study will have adequate power to demonstrate a difference from 13%)
- Overall alpha = 0.025, one-sided
- 10% attrition

With 150 enrolled and treated subjects, minus an assumed 10% attrition rate, the expected number of subjects with 12 months of follow-up at the final analysis is 135.

For the US/Canada/Europe/Japan cohort, 165 treated subjects affords 93% power to test the primary endpoint based on the same assumptions. With 165 enrolled and treated subjects, minus an assumed 10% attrition rate, the expected number of subjects with 12 months of follow-up at the final analysis is 148.

Rationale for Performance Criteria

The safety endpoint definition is based on the Guidance for Industry and FDA Staff²⁰. The estimated safety rate of 5% was selected based on current rate observed in the STOP AF Post Approval Study (PAS). Table 13 summarizes the safety event rate in STOP AF PAS. The safety event rate is 2.3% in STOP AF PAS based on the 2015 FDA Annual Report. The study was not complete and follow-up was ongoing at the time of the 2015 annual report. Therefore the event rate may be slightly higher when the study is completed due to additional events reported, the persistent AF population being studied under this protocol has further advanced AF disease, and therefore the estimated rate for the STOP Persistent AF study has been estimated to be 5%. The OPC of 13% is based on the meaningful clinical difference of 8% (i.e., if the safety rate of the cryoballoon in this population is 5%, the study will have adequate power to demonstrate a difference from 13%)

²⁰ Clinical Study Designs for Percutaneous Catheter Ablation for Treatment of Atrial Fibrillation. January 9, 2004.

Table 13: Safety Event Rate in STOP AF PAS

Study	Observed Safety Event Rate ¹
STOP AF PAS (n=347) ²¹	8 safety events in 8 subjects Safety event rate = 2.3% PNI Unresolved at 12 months (3) Cerebrovascular accident (1) Pericardial Effusion (1) Cardiac tamponade (1) PV Stenosis (1) Incision site hematoma (1)

¹Based on the primary safety endpoint definition in this STOP Persistent AF protocol

²¹ [60 Month Interim Post Approval Study Status Report. PMA P100010/R Arctic Front Cardia CryoAblation System. STOP AF PAS. Version 2, 10DEC2015.](#)

Medtronic Confidential

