13.19. Subject Withdrawal or Discontinuation

A subject can withdraw from the study or the [REDACTED] sub-study at any time. If the subject wishes to exit from the study (i.e. the subject revokes consent), the center is required to document the reason for exit on an eCRF. In addition, centers shall follow the regulations set forth by their IRB/MEC. It is recommended to follow the subject until all ongoing device and/or procedure-related adverse events are resolved or unresolved with no further actions planned. For countries following ISO, permission may be requested to follow-up with the subject outside of the study due to withdrawal based on problems related to the study device safety or performance. Following exit, subjects will continue to receive standard medical care. All data available through the time of the subject's exit will be used for analysis.

Reasons for study exit include:

- Subject lost to follow-up
- Subject did not meet inclusion/exclusion criteria after consent and did not undergo an ablation procedure
- An Arctic Front Advance catheter was not used during the subject's ablation procedure
- Subject did not provide consent or data use protection authorization
- Subject chooses to withdraw (e.g., consent withdrawal, relocation to another geographic location)
- Investigator deems withdrawal necessary (e.g., medically justified, inclusion/exclusion criteria not met, failure of subject to maintain adequate study compliance)
- The sponsor decides the study will be closed or a particular center will be closed

The following information is required to be collected at study exit:

- Reason for exit must be documented on the eCRF and in the subject's medical record

In the case that the subject is determined to be lost to follow-up, details of a minimum of two attempts and the method of attempt (e.g., one letter and one phone record or two letters) to contact the subject must be recorded.

An unscheduled office visit should be attempted if the subject exits the study outside of a scheduled follow-up visit.

14. Risks and Benefits

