15.1. Adverse Event and Device Deficiency Definitions

Where the definition indicates “device”, it refers to any device used in the study. This might be the catheter, or any other component of the system under investigation, or any market-released component of the system.

Table 9: Adverse Event and Device Deficiency Definitions

General	
Adverse Event (AE)	
Any untoward medical occurrence, unintended disease or injury, or untoward clinical signs (including abnormal laboratory findings) in subjects, users or other persons, whether or not related to the investigational medical device
 
NOTE 1: This definition includes events related to the investigational medical device or the comparator. NOTE 2: This definition includes events related to the procedures involved. NOTE 3: For users or other persons, this definition is restricted to events related to investigational medical devices. (ISO 14155:2011, 3.2)

Adverse Device Effect (ADE)	
Adverse event related to the use of an investigational medical device
 
NOTE 1: This definition includes adverse events resulting from insufficient or inadequate instructions for use, deployment, implantation, installation, or operation, or any malfunction of the investigational medical device. NOTE 2: This definition includes any event resulting from an error use or from intentional misuse of the investigational medical device. (ISO 14155:2011, 3.1)

Device Deficiency (DD)	
Inadequacy of a medical device with respect to its identity, quality, durability, reliability, safety or performance.
 
NOTE: Device deficiencies include malfunctions, use errors and inadequate labeling (ISO 14155:2011, 3.15)

Relatedness	
Procedure related	An Adverse Event directly related to any portion of the procedure that encompasses cryoablation.
Cryoablation system related	An Adverse Event that results from the presence or performance (intended or otherwise) of the cryoablation system (including the Arctic Front Advance, Freezor MAX, FlexCath Sheath, Achieve Mapping Catheter, CryoConsole, Manual Retraction Kit)

STOP Persistent AF Clinical Investigation Plan

Version 6.0, 01DEC2017 Page 52 of 128

[REDACTED]	[REDACTED]
Cardiovascular related	An Adverse Event relating to the heart and the blood vessels or the circulation.
Seriousness	

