6.1. Study Subjects

6.1.1. Disposition of Subjects

Subjects included in our primary analysis cohort require all of the following conditions: eligibility, consent to be studied, and treatment pulmonary veins with the Arctic Front Advance Cardiac Cryoablation Catheter System. The study will collect data on subjects who consented to be studied and to the cryoablation procedure, but who were given a different treatment at the time of operation, but these cases will not affect the analysis of primary, secondary, or ancillary objectives, as they do not meet the criteria of undergoing a cryoablation procedure.

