6.1.3. Analysis Sets

=

The **Full analysis set** consists of all enrolled subjects who sign informed consent. The full analysis set will be used for AE reporting in general and ancillary objective [REDACTED]

The **Modified Intention-to-Treat (mITT)** cohort is the subset of subjects who maintain informed consent at least until the index cryoablation procedure was finished. For endpoints analyzed in this group of subjects, the standard Intention-to-Treat (ITT) protocol applies immediately upon insertion of the cryoballoon catheter into the subject's vasculature. The mITT cohort will be used in the analysis of the primary efficacy objective, the secondary objective regarding Quality of Life (QoL), and the ancillary objective [REDACTED]. The mITT dataset will be used in the analysis of the primary efficacy and safety objectives, as well as for the secondary objective and ancillary objectives [REDACTED].

This study has planned submissions to the US FDA and Japan PMDA. The Pre-Market Approval Submission (PMA-S) to the US FDA will include subjects from centers in US and Canada. If full 12-month data is available from Japan subjects at the time of PMA-S submission, the Japan data may be included in the PMA-S submission. The submission to the Japan PMDA will include analysis from data collected from all four geographies. The analyses for both submissions will follow the same pre-specified analysis procedures, so this SAP will not distinguish between the PMDA submission cohort (165 subjects expected) vs. the subset of subjects used for the PMA-S (150 subjects expected) except when differences due to sample size are relevant to the discussion.

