6.2.3.3. Analysis Methods

The probability of a safety event at 12 months (365 days) will be estimated using survival analysis, the Kaplan-Meier method. The standard error will be approximated using Greenwood's formula. A two-sided 95% log-log confidence interval for the probability will be constructed.

For every treated subject, day 0 is defined as the day of the index cryoablation procedure. For subjects with a safety event, the survival date will be set to the date of the safety event. For subjects without a safety event, those subjects will be censored at the last study contact date recorded on CRF which may include the last study visit, the exit date, or death date. If a subject without a safety event is lost to follow-up, the censoring date will be set to the last known study visit date.

For subjects with a repeat ablation within 12 months, the start of the survival analysis will not reset. Day 0 will remain the day of the index cryoablation procedure. Safety events related to the repeat ablation procedure occurring on or prior to 365 days post the index cryoablation procedure will be counted as safety events and count against the primary safety objective. This objective will be analyzed in the mITT dataset: all enrolled subjects who have the Arctic Front Advance Cardiac CryoAblation Catheter inserted into vasculature will be included.

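### The primary safety test leaves out subjects whose procedure is abandoned after an access or sheath complication before the balloon catheter is inserted

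*Protocol*

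**What the plan says.** The primary safety objective in Protocol 17.3.2 is worded for the procedure: "Demonstrate an acceptable safety profile of the pulmonary vein isolation (PVI) ablation procedure". The analysis set in the same section is worded for the device: "All enrolled subjects who have the Arctic Front Advance Cardiac CryoAblation Catheter inserted into vasculature will be included". SAP 6.2.3.3 repeats the rule: "This objective will be analyzed in the mITT dataset: all enrolled subjects who have the Arctic Front Advance Cardiac CryoAblation Catheter inserted into vasculature". SAP 6.1.3 describes the mITT cohort in the same way: "the standard Intention-to-Treat (ITT) protocol applies immediately upon insertion of the cryoballoon catheter".

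Protocol Table 9 (section 15.1) counts an event as procedure-related if it is tied to any part of a procedure that encompasses cryoablation. It defines the cryoablation system as "including the Arctic Front Advance, Freezor MAX, FlexCath Sheath, Achieve Mapping Catheter, CryoConsole, Manual Retraction Kit". Protocol 8.1.1 describes the balloon catheter as reaching the heart from the femoral vessels through a transseptal sheath.

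Two further passages bear on subjects who never receive the balloon catheter. Protocol 13.19 lists this reason for study exit: "An Arctic Front Advance catheter was not used during the subject's ablation procedure". SAP 6.1.1 says of consented subjects who were given a different treatment: "but these cases will not affect the analysis of primary, secondary, or ancillary objectives". For descriptive reporting, SAP 6.1.3 uses all consented subjects: "The full analysis set will be used for AE reporting in general".

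**The concern.** Access, septal crossing and sheath placement come before the balloon catheter enters the left atrium, and they carry risk of their own. An injury at these steps can end the case. The subject then has a complication of the kind listed in the endpoint (perforation, tamponade, effusion, transfused bleeding, stroke, or death within 7 days) but does not enter the analysis set. The set is conditioned on reaching a point inside the procedure whose safety is being assessed.

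A case abandoned because of a listed event can only raise the rate if it is restored, so leaving it out favours meeting the 13% goal. At stake is whether the single confirmatory safety result describes procedures attempted or only procedures that got as far as the balloon catheter.

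**Working it through.** **1. Which subjects are lost.** The rule in Protocol 17.3.2 and SAP 6.2.3.3 selects subjects; it does not select events by time of onset. Day 0 is the calendar day of the index procedure, and nothing requires onset after insertion.
- Sheath or septal injury, balloon catheter then inserted: subject in the set, event counts.
- Sheath or septal injury, case stopped, balloon catheter never inserted: subject and event both out.
- Case stopped with no complication, balloon catheter never inserted: subject out, no event lost.

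Only the second group matters here. For a sheath injury, Table 9 is explicit that the event is system-related. For septal puncture alone in an abandoned case the wording is ambiguous, because the procedure-related definition refers to a procedure that encompasses cryoablation and none took place.

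**2. The plan's own power figure.** Inputs from Protocol 17.3.2 and SAP 7.2: 150 treated, 10% attrition, 5% against 13%, one-sided 0.025, exact binomial.
- 150 × 0.9 = 135 analysed. P(X ≤ 9 | 135, 0.13) = 0.0141; P(X ≤ 10 | 135, 0.13) = 0.0290, which exceeds 0.025. Power = P(X ≤ 9 | 135, 0.05) = 0.860.
- For the PMDA cohort, 148 analysed: P(X ≤ 11 | 148, 0.13) = 0.0233; power 0.932.

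Both match the stated 86% and 93%. The sample size is not in question.

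**3. The decision boundary.** The planned rule is a Kaplan-Meier estimate with Greenwood standard error and a two-sided 95% log-log interval. Assuming no censoring before day 365, with d events in n subjects:

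S = 1 − d/n; w = √[d/(n(n − d))] / |ln S|; upper bound = 1 − S^exp(1.96w).

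- 11/150: S = 0.92667, w = 0.3016, upper bound 12.85%. Met.
- 12/151 (one abandoned case with an event restored to numerator and denominator): S = 0.92053, w = 0.2888, upper bound 13.57%. Not met.
- PMDA cohort: 12/165 gives 12.45% (met); 13/166 gives 13.10% (not met).

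With one, two or three such cases restored to 150 subjects, the total allowed stays at 11 events. The number allowed among balloon-inserted subjects therefore falls to 10, 9 or 8.

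Abandoned cases without an event pull the other way. Adding seven of them to 12/151 gives 12/158, upper bound 12.99%, which meets the goal again.

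**4. How many events could be lost.** The documents give no rate for complications that end a case before insertion, so this step is an assumption. Table 24 in Protocol Appendix G gives 0.53% for pericardial effusion or tamponade and 0.20% for cardiac tamponade. The rows may overlap, and they are not limited to serious events.
- First row only: 150 × 0.0053 = 0.80 events. Both rows: 150 × 0.0073 = 1.10 events.
- Assume that 10% to 50% of these occur before insertion and also end the case without insertion: 0.08 to 0.40 events (one row) or 0.11 to 0.55 (both rows).

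Take lost events as Poisson with mean m and ignore the small change in denominator. The probability that the verdict changes is then Σ over d ≤ 11 of P(Bin(150, p) = d) × P(Poisson(m) ≥ 12 − d). For m from 0.08 to 0.55:
- p = 5% (planning rate): about 0.5% to 3.6%.
- p = 2.3% (Table 13): below 0.1%.
- p = 13%: about 0.1% to 0.5%.

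**The case against.** A set of subjects exposed to the device under study is a defensible choice. Most endpoint windows run from the ablation procedure, and the sizing text in Protocol 17.3.2 speaks of the safety rate of the cryoballoon. Extending the set to attempted procedures changes the estimand and brings in subjects who never met the balloon catheter. This stands as a reason to keep the balloon-inserted set as primary.

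Three stronger readings are tempting, and the documents do not support them.
- *Every complication before insertion is lost.* It is not: if the balloon catheter is later inserted, the event counts.
- *The restriction always lowers the rate.* That holds for abandoned cases with an event. A procedure-begun set would also admit abandoned cases without one, which lower the rate, so the net direction depends on the mix.
- *The events disappear.* They do not. Protocol 15.2 collects adverse events from consent, the Clinical Events Committee adjudicates all procedure- and system-related events and all deaths, Protocol 15.4 asks for continued follow-up of unresolved related events after exit, and the SAP reports adverse events in all consented subjects.

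It could also be argued that SAP 6.4 covers the point, since it places the tipping-point analyses in the full analysis set. However, the method it then describes is for mITT subjects with short follow-up, and its only stated tipping criterion is the 40% efficacy goal. It does not test abandoned cases against 13%.

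**Conclusion.** The concern holds in a narrow form. A subject whose procedure is abandoned after an access, transseptal or sheath complication, with the Arctic Front Advance never inserted, is not part of the primary safety test. For sheath events this conflicts with the protocol's own definition of system-related; for septal puncture alone the definition needs clarifying. Such events would be reported descriptively, but no analysis in the plan tests them against 13%.

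The expected effect is small. Under the assumed shares it is a fraction of one event per 150 subjects, and the chance of a changed verdict is a few percent at most. Those figures rest on an assumed share, on Table 24 rows that may overlap, and on no censoring. That one case decides at the boundary is true of any threshold rule; it shows only that the restriction can matter. This is a cheap improvement to the plan, and it does not call the stated power or the primary analysis into question.

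**What to change.** Pre-specify in the SAP a sensitivity analysis of the primary safety objective in all subjects in whom the study procedure was begun, defined as venous access obtained with intent to use the Arctic Front Advance. Set day 0 as the day of the attempt, use the same Kaplan-Meier log-log method and 13% rule, and report the result beside the balloon-inserted primary analysis. State whether an event in an abandoned attempt counts as procedure-related under Table 9.

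In the same revision, reconcile the SAP's entry criteria. Section 6.1.1 requires that pulmonary veins were treated, the mITT definition in 6.1.3 opens with consent kept until the procedure was finished, and 6.2.3.3 requires only insertion. Read literally, 6.1.1 would also remove a subject in whom the balloon catheter was inserted but no vein was treated.

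The cost is wording and one extra table; the adverse event data are already collected from consent. The downsides are that a few subjects never exposed to the balloon catheter enter that denominator, that abandoned cases without an event slightly lower the rate, and that subjects exited soon after an abandoned attempt would be censored early.
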